COVER PAGE for Study Protocol

Title: Using Pressure Detecting Insoles to Reduce Knee Loading

NCT number: NCT02955225

Document date: June 5, 2017

Study Protocol

This is a randomized, placebo controlled, longitudinal pilot study.

After a telephone prescreening, an in-person visit will be performed to screen for inclusion and exclusion criteria, including a clinical and radiographic assessment, and to identify the index knee (defined as the more painful knee in the case of bilateral knee OA). A total of 40 subjects with symptomatic and radiographic medial knee OA will be enrolled in the study and obtain a standardized flexible shoe ('Mobility shoe', [name]). A standing radiograph of the knees will be taken at a screening visit to assess for the existence of knee OA. The 40 subjects will be randomized into two unequal groups: group A will consist of 25 subjects who will train in the mobility shoe with active pressure-based feedback from a pressure-detecting shoe insole (OpenGo, Moticon GmbH, Munich, Germany), and group B will consist of 15 subjects who will train in the same mobility shoe with a deactivated insole.

A total of three study visits will occur at the following time points: baseline, 3 weeks, and 6 weeks. At all three visits, the following outcome variables will be acquired: (1) joint loads using 3D motion analysis of in subjects' gait both in their own shoes and the mobility shoe with inactive insole, and (2) knee symptoms, stiffness, pain, daily function, recreational function, and quality of life using the Knee Injury and Osteoarthritis Outcome Score (KOOS). At the 3 and 6 week visits only, additional data from the insole will provide medial-lateral pressure distribution, total time walking and total steps during walking in the and time spent using shoe and insole.

After enrollment, all subjects will return for the baseline visit within three months. At baseline, subjects in both groups will receive their personal mobility shoe, complete the KOOS, and undergo a baseline motion analysis. Subjects in group A will receive the active OpenGo insoles, in addition to a study-issued Android-based (Android 4.3) smartphone (xperia Z1, Sony, Tokyo) containing a preloaded application (MoticonApp, Moticon Gmbh, Munich, Germany) and without a Subscriber Identity Module (SIM) card (and, therefore, no data or cell phone use), which will provide pressure-based feedback for their index limb, and record the time, steps, and center of pressure (COP) during walking. During this visit, they will receive training by a licensed physical therapist on the use and maintenance of the insole, and they will be given a supply of replacement coin-cell batteries (although it is unlikely that batteries have to be replaced during the 3-week testing interval). The subjects in group A will be asked to train in the combined shoe/insole device for 3x5 min per day, at least 6 days a week for 3 weeks. Subjects in group B will receive the inactive OpenGo insole, which will not provide feedback but will be set in record mode. All subjects will be encouraged to wear the study shoes as their primary form of footwear and for a minimum of 6 hours/day, 6 days/week. They will be given a diary to record the daily time spent wearing the shoe/insole, daily analgesic history, and adverse events. These diaries will be reviewed at the 3 and 6 week study visits. At the 3 week visit, 3D motion analysis will be assessed and the KOOS will be repeated. During this visit, the feedback component in group A's insole will be deactivated but will continue to be recordingcapable. From the second visit at week 3 until the third visit at week 6, both groups will

continue to walk with mobility shoe with a recording but otherwise inactive insole. These final 3 weeks will assess for the integration of a new movement pattern in group A. After completing the final KOOS and 3D motion analysis during the third visit, subjects will have completed the study.

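### KOOS arm comparison: the SAP states no baseline adjustment, and no KOOS is named at the screening visit; adjusting for baseline brings most of the gain, and a screening KOOS may add a little

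*Protocol*

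**What the plan says.** The Study Protocol describes a telephone prescreen and then a screening visit: "an in-person visit will be performed to screen for inclusion and exclusion criteria, including a clinical and radiographic assessment". The index knee is identified there, and is the more painful one when both knees are affected. Baseline comes later: "After enrollment, all subjects will return for the baseline visit within three months".

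The outcome schedule starts at baseline: "A total of three study visits will occur at the following time points: baseline, 3 weeks, and 6 weeks". For joint loads and the KOOS the protocol adds: "At all three visits, the following outcome variables will be acquired". The first KOOS named falls at the visit where the study footwear is issued: "At baseline, subjects in both groups will receive their personal mobility shoe, complete the KOOS, and undergo a baseline motion analysis". The contents of the screening clinical assessment are not itemised, so a KOOS there is not named rather than expressly excluded.

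The SAP assigns paired t-tests to the primary hypothesis, which it does not state. It assigns mixed ANOVAs to the longitudinal comparison of knee loading or questionnaire scores between the two conditions, and correlations to changes in KOOS subscales and knee loads. It mentions neither a baseline covariate nor a second pre-treatment value.

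**The concern.** The KOOS comparison rests on 25 against 15 subjects, so precision is limited. In a comparison of changes from one baseline score, all of the measurement error in that score enters every change. Two inexpensive remedies are unused: adjusting for the baseline value already collected, and taking one more value at a visit that every subject attends anyway.

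There is also a question of interpretation. Both arms receive the mobility shoe at baseline and are encouraged to make it their main footwear, so group B shows change with the shoe, not change without intervention. The only interval free of study footwear lies before baseline, and no KOOS is named at its start. Subjects enter because they are symptomatic, so some movement in scores after entry is to be expected and would go unseen.

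**Working it through.** **Inputs.** From the protocol: 25 and 15 subjects, 40 in all; baseline up to three months after enrollment. The documents give no alpha, power, KOOS SD, target difference or correlation between visits, so there is no stated figure to reproduce. Assumed: results in SD units, equal variance at each visit, no dropout, two-sided 5% and 80% power where a detectable difference is quoted, and the correlations shown.

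**Step 1: baseline as covariate, no new data.** In a mixed ANOVA, the group-by-time contrast of one follow-up against baseline is a comparison of change scores. With correlation ρ between baseline and follow-up:

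- change score: variance = 2(1−ρ)
- baseline-adjusted: variance = 1−ρ²
- ratio = (1+ρ)/2

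At ρ = 0.6, 0.7 and 0.8 the ratio is 0.80, 0.85 and 0.90: variance lower by 20%, 15% and 10%. Over ρ = 0.5 to 0.9 the reduction runs from 25% to 5%. Estimating the covariate's slope costs a factor of about 37/36 = 1.028, so the three ratios become about 0.82, 0.87 and 0.925.

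In SD units, the standard error is √variance × √(1/25 + 1/15) = 0.327 × √variance. At ρ = 0.7 the detectable difference is (1.960 + 0.842) × 0.327 × √0.60 = 0.71 SD for change scores, and with √0.51 it is 0.65 SD after adjustment (0.66 with the 37/36 factor).

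**Step 2: screening KOOS as a second covariate.** Let r, s and t be the baseline–follow-up, screening–baseline and screening–follow-up correlations. The residual variance is

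1 − (r² + t² − 2rst)/(1 − s²),

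to be compared with 1 − r². The second covariate costs a further factor of 36/35 = 1.029.

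| r | s | t | Ratio to baseline only | Net of 36/35 |
|---|---|---|---|---|
| 0.70 | 0.60 | 0.60 | 0.901 | 0.926 |
| 0.70 | 0.60 | 0.55 | 0.948 | 0.975 |
| 0.75 | 0.70 | 0.65 | 0.930 | 0.957 |
| 0.70 | 0.70 | 0.49 (decay with time) | 1.000 | 1.029 |

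In the first three rows the net gain is about 2.5% to 7% of variance, or 1% to 4% of the standard error. In the last row, screening carries nothing beyond baseline and the lost degree of freedom makes the result about 3% worse.

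**Step 3: averaging the two values.** Under decay (0.70, 0.70, 0.49), the variance of change from the two-value mean is 1 + (1 + 0.70)/2 − (0.70 + 0.49) = 0.66, against 0.60 for change from baseline alone. The standard error rises by √(0.66/0.60) − 1 = 4.9%. Averaging can therefore harm, which is why separate covariates are preferable.

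**Step 4: what the pre-baseline change can show.** Over 40 subjects at ρ = 0.7, its 95% half-width is 1.96 × √(2 × 0.3/40) = 0.24 SD (0.31 at ρ = 0.5, 0.14 at ρ = 0.9).

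**The case against.** One pre-treatment questionnaire is an ordinary design for a pilot, and the documents set no precision goal for the KOOS that the schedule could fail. That stands: this is an improvement, not an error.

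Randomization protects the arm comparison. Group B has the same shoe and the same KOOS visits, so drift and regression to the mean are expected equally in both arms. That also stands. A reader might infer that the missing screening KOOS biases the comparison, but the design does not support this. Nor do the documents tie the paired t-tests to the KOOS: they serve an unstated primary hypothesis in a study titled for knee loading.

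Two further stronger readings are tempting:

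- **A large gain from screening.** If all visits were equally correlated, two covariates would cut variance by 14%, 17% and 20% at ρ = 0.6, 0.7 and 0.8, and averaging two values would cut change-score variance by 25%. But equal correlation requires a score taken up to three months before baseline to predict follow-up as well as baseline does. That sits badly with the worry that scores drift over that gap. The 25% belongs to averaging, which can also do harm.
- **A direct reading of untreated change.** The gap before baseline varies between subjects, while treatment intervals are fixed at three weeks. Subjects are also selected as symptomatic, so the change mixes natural drift with regression to the mean.

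Finally, the screening assessment might already include a symptom score. Even so, the SAP does not say how it would be used.

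**Conclusion.** The point holds as a minor improvement. The more dependable gain is baseline adjustment of the KOOS arm comparison: 10% to 20% less variance than change scores at ρ = 0.6 to 0.8, or about 7% to 18% after the degree of freedom. The screening KOOS adds between a 3% loss and a 7% gain, depending on how well it predicts follow-up. All of these sizes rest on assumed correlations. The screening-to-baseline change has descriptive value, because neither arm is free of the study shoe after baseline, but it cannot serve as an untreated control. Nothing here bears on joint loads, which need motion analysis.

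**What to change.** 1. In the SAP, specify that the KOOS arm comparison at follow-up uses baseline KOOS as a covariate. Cost: a line of text and one degree of freedom.
2. In the protocol, add a dated, self-completed KOOS for the index knee at the in-person screening visit. If one is already taken there, name it. Cost: a few minutes per subject, including those who then fail screening; no extra visit.
3. In the SAP, enter the screening KOOS as a second, separate covariate and do not average it with baseline. Cost: one further degree of freedom, about 3% of variance, which is not recovered if the screening value adds no prediction.
4. Report the screening-to-baseline change descriptively with the interval in days, stating that it mixes drift with regression to the mean over a variable gap. Do not subtract it from the change on treatment.

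If only one change is made, it should be the first.

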COVER PAGE for Statistical Analysis Plan

Title: Using Pressure Detecting Insoles to Reduce Knee Loading

NCT number: NCT02955225

Document date: May 12, 2015

Statistical Analysis Plan

To address the primary hypothesis we will use paired t-tests. Separate mixed ANOVAs will be used to evaluate either differences in knee loading or questionnaire scores between the two treatment conditions longitudinally. Pearson or Spearman correlations will be used to evaluate associations between changes in subsections of the KOOS questionnaire and knee loads.

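### The SAP tests an unstated primary hypothesis with paired t-tests and does not say that the randomised comparison decides a claim about feedback

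*SAP*

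**What the plan says.** The SAP is three sentences long. The first reads "To address the primary hypothesis we will use paired t-tests". No hypothesis is stated there or in the protocol, and no primary variable, footwear, visit, pair of measurements or analysis set is named. The second reads "Separate mixed ANOVAs will be used to evaluate either differences in knee loading or questionnaire scores between the two treatment conditions longitudinally". The third concerns correlations between KOOS changes and knee loads.

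The protocol opens with "This is a randomized, placebo controlled, longitudinal pilot study" and continues "The 40 subjects will be randomized into two unequal groups": 25 with active feedback (group A) and 15 with a deactivated insole (group B), in the same mobility shoe. On timing it says "A total of three study visits will occur at the following time points: baseline, 3 weeks, and 6 weeks". At each visit joint loads come from "gait both in their own shoes and the mobility shoe with inactive insole". Group A's system is one "which will provide pressure-based feedback for their index limb". For both arms, "All subjects will be encouraged to wear the study shoes as their primary form of footwear".

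**The concern.** A paired t-test compares two measurements within the same subject, so it makes no use of the randomised comparison. If the primary hypothesis is that feedback lowers knee loading, which the randomised, placebo-controlled design suggests, a significant paired test in group A would not establish it. Group B receives the same new shoe, the same encouragement to wear it and the same repeated gait testing, so a change common to both arms could produce the result.

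The SAP also plans an analysis that does compare the arms, and does not say which of the two governs. If the paired test is significant and the mixed ANOVA shows no difference between arms, the plan gives no rule. A reader of the report could not tell a before-after change from an effect of feedback.

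**Working it through.** The documents give no alpha, power, effect size or SD, so there is no planned calculation to reproduce. The only sum to check, 25 + 15 = 40, agrees.

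**1. Does any natural paired test of joint loads contrast the arms?** There are 3 visits and 2 footwear conditions. Visit against visit in the same footwear gives 3 × 2 = 6 pairs; shoe against shoe at the same visit gives 3. All are within-subject.
- Visit pairs mix feedback with anything else that changes over time.
- Shoe pairs measure footwear, and the mobility shoe is tested with the insole inactive.
- Index limb against other limb is conceivable, since feedback is for the index limb. The documents do not say that the other limb is analysed, and this pair would not contrast the arms either.

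**2. What does the mixed ANOVA leave open?** With 2 groups and 3 visits, the group-by-time interaction has (2 − 1)(3 − 1) = 2 degrees of freedom, and the group main effect averages over baseline as well as follow-up. The SAP names neither term, nor a visit or footwear.

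**3. Size of the problem if the claim is about feedback.** Assumptions: two-sided 5%, full completion, no feedback effect, and a change d shared by both arms in SDs of the change score. The values of d are illustrative.

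Paired test: non-centrality d√n on n − 1 df. Between-arm t-test on change: the shared d cancels, so the non-centrality is 0 on 38 df.

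| Shared d | Non-centrality, n = 25 | Group A paired test significant | All 40 pooled, paired test significant | Between-arm test significant | Group A significant, between-arm not |
|---|---|---|---|---|---|
| 0.2 | 1.0 | 16% | 23% | 5% | 14% |
| 0.3 | 1.5 | 30% | 46% | 5% | 28% |
| 0.5 | 2.5 | 67% | 87% | 5% | 64% |

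The last column is by simulation. In simulation, baseline-adjusted ANCOVA also held its level (0.049 to 0.053).

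**4. Sensitivity of each test.** Same alpha, 80% power, effects in SDs of change.
- Group A paired, n = 25: detectable 0.58; 95% CI half-width 2.064/√25 = 0.41.
- Between arms, unadjusted: √(1/25 + 1/15) = 0.327; detectable 0.94; half-width 2.024 × 0.327 = 0.66; power at 0.5 SD 32%.
- Between arms, ANCOVA: the residual SD relative to the SD of change is √((1 + ρ)/2), where ρ is the assumed baseline to follow-up correlation. Variance is multiplied by 1 + 1/36 for chance baseline imbalance, on 37 df.

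| ρ (assumed) | Residual SD | Detectable at 80% | Half-width | Power at 0.5 SD |
|---|---|---|---|---|
| 0.5 | 0.866 | 0.83 | 0.58 | 40% |
| 0.7 | 0.922 | 0.88 | 0.62 | 36% |
| 0.9 | 0.975 | 0.93 | 0.65 | 33% |

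**The case against.** The strongest reply is that the primary hypothesis may be within-subject. The title names no comparator, allocation favours group A, and the protocol describes the last three weeks as a test of integration in group A. A paired test would then fit, and this is a self-described pilot with little between-arm power. That stands as far as it goes: the documents do not show that the paired test is wrong. But the hypothesis is still unstated, and a within-subject result would not estimate the effect of feedback.

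A second reply is that the feedback analysis is already there. This also stands in part. A reader might infer that the plan lacks a between-arm analysis, or that the mixed ANOVA has nothing to do with feedback. Neither is supported: it compares the two conditions, and these differ by whether the insole gives feedback. What it lacks is rank and a named contrast.

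A reader might also infer that no within-subject comparison of feedback on and off is possible. That holds only for motion-analysis loads. The insole records in group A both while feedback is active and after it is switched off at week 3, so insole data could supply such a pair. That pair, too, would leave out group B.

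Finally, the shared changes of 0.2 to 0.5 SD have no source in the documents. They show how the two tests behave and predict nothing about this trial.

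**Conclusion.** The point holds as a gap in decision rules. The SAP gives the primary hypothesis to a test that does not use the randomised comparison, does not state that hypothesis, and leaves the existing between-arm analysis unranked and without a decisive term, visit or footwear. If the claim is about feedback, relying on the group A paired test would give a significant result 16% to 67% of the time with no feedback effect, under an assumed shared change of 0.2 to 0.5 SD, against 5% for the between-arm test.

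The textual finding needs none of these assumptions; the percentages depend on all of them. A reader might go further and infer that the open choice of pair means the sponsor would select one after seeing results. The documents give no sign of that, and it forms no part of this conclusion. Nor is any stated power broken, since none is stated. The point should be fixed, but it does not invalidate the design, which already collects the data for the right comparison.

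**What to change.** State the primary hypothesis, then add one of two texts.

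*If the claim is about feedback:* any claim that feedback reduces knee loading is decided by the group A versus group B contrast for [one index-limb load variable] in [one footwear condition] at [one visit]. It is estimated by ANCOVA adjusted for baseline in the same footwear, or by the one-degree-of-freedom group-by-time contrast of the planned mixed ANOVA, and reported with a 95% CI. Within-arm paired t-tests are supportive only.

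*If the hypothesis is within-subject:* keep the paired t-test as primary, name the two measurements and the analysis set (group A, or both arms), and state that this test does not estimate the effect of feedback and that the mixed ANOVA group contrast does.

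The sponsor chooses the hypothesis and the visit: week 3 closes the feedback period, and week 6 addresses integration of the new pattern.

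The change needs no new data or visits. It should be made before outcomes are seen by arm; if they have been seen, the report should say that the choice was not pre-specified. A within-subject hypothesis loses nothing. A feedback hypothesis loses sensitivity: 80% power is reached at about 0.83 to 0.94 SD of change, against 0.58 SD for the group A paired test. This pilot should therefore put its weight on the estimate and its interval, not on significance.

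### The only between-arm analysis is a mixed ANOVA with no missing-data rule; in its usual complete-case form it would drop observed week-3 data for anyone lost before week 6

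*SAP*

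**What the plan says.** The SAP is three sentences long. The first covers the primary question: "To address the primary hypothesis we will use paired t-tests". The second is the between-arm analysis: "Separate mixed ANOVAs will be used to evaluate either differences in knee loading or questionnaire scores between the two treatment conditions longitudinally". The third covers correlations between KOOS changes and load changes. The SAP does not say which visits form the time factor, how the ANOVA is fitted, who is analysed, or what happens when a visit is missed.

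The Protocol (Study Protocol, visit paragraph) sets the schedule: "A total of three study visits will occur at the following time points: baseline, 3 weeks, and 6 weeks". Joint loads and KOOS are collected each time: "At all three visits, the following outcome variables will be acquired". Group A's feedback is switched off at the week-3 visit, and the Protocol says of what follows: "These final 3 weeks will assess for the integration of a new movement pattern in group A". Week 3 is therefore the end-of-training measurement and week 6 the retention measurement.

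On size, the Protocol says "A total of 40 subjects with symptomatic and radiographic medial knee OA will be enrolled in the study", split so that "group A will consist of 25 subjects who will train in the mobility shoe with active pressure-based feedback" and "group B will consist of 15 subjects who will train in the same mobility shoe with a deactivated insole". Neither document gives a dropout allowance, a missing-data rule, or a statement on keeping or discarding the data of subjects who withdraw.

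**The concern.** With loads and KOOS measured at three visits, the natural reading of a longitudinal mixed ANOVA is a split-plot analysis with arm between subjects and visit within subjects. In its standard form it uses only subjects with a value at every visit. A missing week-6 value then removes the subject's baseline and week-3 values as well.

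That matters here because the two follow-up visits answer different questions. What a subject does after feedback ends should not decide whether their end-of-training measurement counts. Only group A loses an active component at week 3, so withdrawal that differs by arm is plausible, though the documents cannot establish it. At best, complete-case deletion wastes valid week-3 data in a trial of 40. At worst, it lets later withdrawal distort the comparison of active with deactivated insole at the end of training.

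**Working it through.** The documents contain no power calculation, SD, correlation or dropout rate. The only planned figure to reproduce is enrolment: 25 + 15 = 40, which agrees.

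**Inputs from the Protocol:** 25 in A, 15 in B; visits at baseline, week 3 and week 6.

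**Assumptions, for illustration only:** SD 1 at each visit; correlation 0.7 between any two visits (0.5 as a check); lower values are better, as for knee load; all losses occur after week 3; contrasts are A minus B in change from baseline.

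**1. Random loss.** The SE of the week-3 contrast is proportional to sqrt(1/nA + 1/nB). With everyone included this is sqrt(1/25 + 1/15) = 0.3266.

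| Lost (A+B) | Left (A, B) | Week-3 records discarded | sqrt(1/nA + 1/nB) | Ratio to 0.3266 |
|---|---|---|---|---|
| 0+0 | 25, 15 | 0 | 0.3266 | 1.00 |
| 2+1 | 23, 14 | 3 | 0.3390 | 1.04 |
| 4+2 | 21, 13 | 6 | 0.3529 | 1.08 |
| 5+3 | 20, 12 | 8 | 0.3651 | 1.12 |

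Random loss costs precision but causes no bias.

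**2. Selective loss in A only.** The change from baseline has SD sqrt(2 x (1 - 0.7)) = sqrt(0.6) = 0.775. The poorer-responding half of a normal distribution lies on average 0.798 SD from the mean, so 0.798 x 0.775 = 0.618. If 4 of 25 leave from that half, the mean of the remaining 21 moves by 0.618 x 4/21 = 0.118, towards a larger apparent benefit. The regression slope of week-6 change on week-3 change is (1 - 0.7)/0.6 = 0.5, so the week-6 shift is 0.5 x 0.118 = 0.059.

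- With 2 lost from A: 0.618 x 2/23 = 0.054 at week 3.
- With 5 lost from A: 0.618 x 5/20 = 0.155 at week 3.
- With correlation 0.5 and 4 lost: the change SD is 1, so 0.798 x 4/21 = 0.152 at week 3 and half of that, 0.076, at week 6.

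**3. The same selection in B.** If 2 of 15 also leave B from its poorer half, B moves by 0.618 x 2/13 = 0.095. The net week-3 bias is 0.118 - 0.095 = 0.023 SD.

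**4. Direction.** If only B loses its 2 poorer responders, B looks better by 0.095 SD and the A-B benefit is understated by that amount. If 4 of A's better responders leave, the benefit is understated by 0.118.

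**5. Scale.** The full-data SE of the week-3 contrast is 0.775 x 0.3266 = 0.253, so a bias of 0.118 is 0.118/0.253 = 0.47 of one SE.

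**6. Simulation check** (correlation 0.7, true effect -0.50 SD at both follow-up visits, 5,000 replicates).

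- Five losses in A only, weighted towards poor week-3 change: complete-case means of -0.68 at week 3 and -0.59 at week 6.
- The same weighting in both arms (5+3): -0.51 and -0.50.
- Random loss (5+3): -0.49 at both visits, with the SD of the week-3 estimate rising from 0.254 to 0.288.
- A separate set of 400 runs of the A-only case: complete-case -0.66 and -0.59; a REML random-intercept model on all observed visits -0.47 and -0.50. All week-3 data also averaged -0.47 in those runs, so the model recovered what full week-3 data would have shown.

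In these runs dropout depended only on observed data. The recovery at week 6 holds under that condition and does not show what happens without it.

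**The case against.** The strongest reply is that the SAP does not say complete cases will be used. A reader might infer that the ANOVAs require all three visits and that week-3 data will be discarded. The documents do not support that as fact. Separate baseline/week-3 and baseline/week-6 ANOVAs, or a REML fit, would satisfy the same sentence and keep the week-3 data. This stands: the risk is conditional on the usual fit. It does not remove the point, because nothing in either document rules that fit out, and the choice could be made after the withdrawals are known.

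Four further objections also stand in part.

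- The primary hypothesis is assigned to paired t-tests. The SAP does not say which visits or conditions are paired, but a baseline-to-week-3 pair would keep subjects lost later. The concern is confined to the between-arm analysis.
- A subject with no week-6 visit has no week-6 value under any method. A reader might blame the ANOVA for a completers-only retention result, but the absence of those values is not its doing. What complete-case ANOVA forgoes is the use of observed week-3 data to adjust the week-6 contrast.
- A reader might infer that any response-related withdrawal overstates the effect. Steps 3 and 4 of the working show otherwise: similar selection in both arms nearly cancels, and other patterns understate the effect.
- This is a six-week, three-visit pilot, and losses may be few. With no losses after week 3, this problem does not arise.

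**Conclusion.** The point holds in conditional form. The SAP's only between-arm method leaves time levels, analysis set and missing-data handling open. In its usual complete-case form it would remove observed end-of-training data because of a later missed visit.

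Under assumed losses of 2+1 to 5+3, the firm cost is a week-3 SE about 4% to 12% larger. Bias is possible but not established. It needs response-related loss that differs between arms, and its sign depends on who leaves. The 0.12 SD (week 3) and 0.06 SD (week 6) figures assume correlation 0.7 and selective loss of 4 of 25 in group A alone. With similar selection of 2 of 15 in group B, the week-3 figure is about 0.02 SD.

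It would also go too far to conclude that a likelihood model fully repairs the retention result. It does so only if withdrawal depends on what was observed up to week 3. If subjects leave because of changes after feedback ends, the week-6 contrast can remain biased. The change is worth making, but the documents do not show that the planned results would be wrong.

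**What to change.** Replace the mixed ANOVAs with a likelihood-based mixed model for repeated measures, one for each knee-load or questionnaire outcome. Each model has arm, visit and arm-by-visit terms, a stated within-subject covariance structure, and a small-sample degrees-of-freedom correction such as Kenward-Roger. Name the visits in the model (baseline, week 3, week 6) and report the arm contrast at week 3 and at week 6 separately. Include every randomised subject with any observed visit, in the assigned arm. Report the number per arm contributing at each visit. State that the analysis assumes missing-at-random and that the week-6 contrast may still be biased if withdrawal depends on unobserved changes after week 3.

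The cost is a few sentences in the SAP, with no new data. The price is the missing-at-random assumption and a covariance structure to be estimated from 40 subjects. Asking subjects who stop training or stop wearing the insole to attend the remaining visits would reduce the missing data itself. That is an optional addition: it changes the Protocol and trial conduct, so it is more than SAP wording.

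### The between-arm mixed ANOVAs share one variance across arms of 25 and 15; if feedback widens group A's response they lose power, and arm-specific variances cost little

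*SAP*

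**What the plan says.** The Study Protocol section describes the design as follows: "This is a randomized, placebo controlled, longitudinal pilot study". It fixes the allocation: "The 40 subjects will be randomized into two unequal groups: group A will consist of 25 subjects", who train with active feedback, while "group B will consist of 15 subjects who will train in the same mobility shoe with a deactivated insole". Outcomes are measured repeatedly: "A total of three study visits will occur at the following time points: baseline, 3 weeks, and 6 weeks".

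The SAP has three sentences of method. The first assigns the primary hypothesis to a within-subject test: "To address the primary hypothesis we will use paired t-tests". The second is the only stated comparison between arms: "Separate mixed ANOVAs will be used to evaluate either differences in knee loading or questionnaire scores between the two treatment conditions longitudinally". The third concerns correlations.

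Neither document mentions a check of equal variance, a covariance structure, arm-specific variances, a Welch or robust alternative, an alpha level, an SD or a power calculation. The SAP does not use the term pooled variance. That is the standard assumption of a classical mixed ANOVA, and reading it into the plan is an inference.

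**The concern.** A classical mixed ANOVA estimates one error variance from both arms together. With equal arms this does little harm even when the spreads differ, because the pooled standard error of the difference is then right on average. With 25 and 15 it is not: the pooled estimate takes most of its information from the larger arm, whereas the true standard error depends more on the smaller one.

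There is a plausible reason for the spreads to differ here. Only group A trains with feedback, and subjects may learn from it and adhere to it to different degrees. Group B has no counterpart to that source of variation. If this makes group A's changes more variable, the larger arm is the noisier one, the standard error is overstated, and a 40-subject pilot gives up power it could keep. If feedback instead made group A more uniform, the standard error would be understated. What is at stake is the between-arm p-values and confidence intervals for knee load and KOOS, the only results that use the randomised control.

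**Working it through.** **Inputs from the documents.** n_A = 25, n_B = 15 and three visits (protocol); mixed ANOVA between arms (SAP). There is no power, SD or effect size in the plan to reproduce.

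**Assumptions.** Two-sided alpha 0.05, normal data, all 40 analysed. The SD ratio between arms is unknown; 1.2 and 1.5 in each direction are the main cases.

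**Step 1: bias of the pooled standard error (change scores).**

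V_pooled = [(n_A − 1)s_A² + (n_B − 1)s_B²]/(n_A + n_B − 2) × (1/n_A + 1/n_B)

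V_true = s_A²/n_A + s_B²/n_B

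For s_A = 1.5 and s_B = 1:

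- V_pooled = (24 × 2.25 + 14)/38 × (1/25 + 1/15) = 1.789 × 0.1067 = 0.1909.
- V_true = 2.25/25 + 1/15 = 0.1567.
- SE ratio = √(0.1909/0.1567) = 1.10, so the standard error is about 10% too large.
- The critical value 2.024 (38 df) then acts like 2.024 × 1.104 = 2.23.

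| s_A : s_B | V_pooled | V_true | SE ratio | Effective critical value | Type I error, pooled (simulated) | Welch (simulated) |
|---|---|---|---|---|---|---|
| 1.2 : 1 | 0.1363 | 0.1243 | 1.05 | 2.12 | 4.1% | 5.0% |
| 1.5 : 1 | 0.1909 | 0.1567 | 1.10 | 2.23 | 3.2% | 5.0% |
| 1 : 1.2 | 0.1240 | 0.1360 | 0.95 | 1.93 | 6.1% | 5.0% |
| 1 : 1.5 | 0.1558 | 0.1900 | 0.91 | 1.83 | about 7.5% | 5.0% |

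Over a wide range of ratios A/B, from 1/3 to 3, the pooled error runs from 11.6% down to 1.9%, while Welch stays at 5.0 to 5.1%. With 20 per arm, V_pooled = (s_A² + s_B²)/20 = V_true, so the exposure comes from the unequal split.

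**Step 2: power when group A is the more variable arm.** Take s_A = 1.5 s_B and a true difference of 1.0 group B SD. The difference is 1/√0.1567 = 2.53 true standard errors. The pooled test needs about 2.23, giving roughly Φ(0.30) = 62%. Welch needs about 2.03, giving roughly Φ(0.50) = 69%. Simulation gives 62% and 69%, a loss of about 7 points. At ratio 1.2 and a difference of 0.94 group B SD the figures are 70.7% and 73.4%, a loss of 2.7 points.

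**Step 3: the group-by-time F test of a three-visit mixed ANOVA.** With compound symmetry and one arm's SD scaled by 1.5 at every visit, simulated type I error at 25:15 is 2.7% (A larger) and about 8.5% (B larger). At 20:20 it is about 5%. If the extra spread appears only after baseline, with a change-score SD ratio of 1.5, the figures are 3.5% and 8.0%. Part of that 8.0% is not due to the split: with the same extra spread in both arms the F test already runs at 5.8%, because sphericity fails.

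**Step 4: cost of the remedy if variances are equal.** At a difference of 0.94 SD, power is 80.1% pooled and 79.4% Welch, a cost of 0.7 points. Over differences from 0.5 to 1.35 SD the largest cost is about 0.75 points. A baseline-adjusted contrast at a single visit with arm-specific variances held 5% error and cost about 0.8 points. With dropout to 20:12 the Welch cost is about one point (61.4% against 60.4% at 0.85 SD). At alpha 0.01 with 25:15 it is 1.3 to 1.7 points. A full repeated-measures model with arm-specific variances was not simulated.

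**The case against.** The strongest reply is that nothing in the documents shows unequal spread. The ratio of 1.5 is an assumption, and at 1.2 the effect is small. This stands, and it makes the point conditional.

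A reader might infer that the plan loses control of false positives. The documents do not support that. If feedback does nothing to anyone, randomisation makes the arms identically distributed and the pooled test runs at about 5%. Inflation needs feedback to narrow the spread while leaving the mean unchanged. In the more plausible direction the test is conservative, and the loss is power.

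A reader might also infer that the trial's primary result is at risk. It is not: the SAP gives the primary hypothesis to paired t-tests, which this issue does not touch.

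A third reply is that the SAP is a short summary, so its silence on variance structure is not a chosen assumption. That is fair. But mixed ANOVA is a named method whose usual form pools, and nothing in the plan says otherwise.

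Lastly, the small cost was checked for Welch and for a single-visit adjusted contrast, not for the full longitudinal model. That stands as a limit on the cost claim. It does not defeat the proposal, because both checked versions are available as the planned analysis.

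**Conclusion.** The point holds as a modest, conditional improvement to the non-primary between-arm analyses. If group A's response is the more variable, the pooled test is conservative: about 4.1% at ratio 1.2 and 3.2% at 1.5 for change scores, and 2.7% at 1.5 for the group-by-time F. It loses about 7 points of power at ratio 1.5. In the less likely reverse case the error is about 6.1% and 7.5%, and about 8.5% for the F test. These figures rest on assumed SD ratios, normal data, a two-sided 5% level, complete data and the classical reading of mixed ANOVA. The case for acting does not depend on evidence of unequal variance, because the protection costs so little if the variances turn out equal.

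**What to change.** In the SAP, state that the between-arm contrasts at week 3 and week 6 will be baseline-adjusted, with a separate residual variance for each arm and Satterthwaite or Kenward-Roger degrees of freedom. If a simpler test is preferred, name Welch's test on the change scores. Make this the planned analysis rather than a fallback chosen after a test of equal variances.

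The change is SAP wording and one model option, with no extra subjects, visits or measurements. The price is slightly fewer degrees of freedom; the power cost under equal variances is the one worked out in step 4. If the full repeated-measures version is chosen, its error rate with 15 subjects in group B should be checked by simulation before it is fixed.
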